5.3.6.2. Endpoints Related to Reduction of Signs and Symptoms and Physical Function

In this study, Other Efficacy endpoints for reduction of signs and symptoms and physical function include those related to ACR responses, HAQ-DI, DAS28 (CRP), modified PsARC, enthesitis (LEI), dactylitis, mCPDAI, DAPSA, MDA, and VLDA.

All Other Efficacy endpoints related to reduction of signs and symptoms and physical function will be conducted under the mFAS population for Adjusted Composite Estimand, and mFAS-UKR for Treatment Policy Estimand, unless explicitly stated otherwise.

5.3.6.2.1. ACR Related Endpoints

ACR 20 response was previously defined in Section 5.3.4.1. ACR 50 and ACR 70 responses are defined similarly to ACR 20 response, except that the improvement threshold of 20% from baseline in ACR 20 response is replaced by 50% and 70%, respectively.

The ACR related Other Efficacy endpoints include:

- Proportions of participants who achieve ACR 20, ACR 50, and ACR 70 responses by visit over time through Week 156.

- Proportion of participants who maintain an ACR 20 response at Week 48, Week 96, and Week 156 among the participants who achieved an ACR 20 response at Week 24.
- Proportion of participants who maintain an ACR 50 response at Week 48, Week 96, and Week 156 among the participants who achieved an ACR 50 response at Week 24.
- Proportion of participants who maintain an ACR 70 response at Week 48, Week 96, and Week 156 among the participants who achieved an ACR 70 response at Week 24.
- Value, change, and percent change from baseline in ACR components by visit over time through Week 156.

5.3.6.2.2. HAQ-DI Related Endpoints

HAQ (Fries 1980) disability index (HAQ-DI) score is an evaluation of the functional status for a participant. CCI

[figure not shown]
[figure not shown]

5.3.6.2.3. DAS28 (CRP) Related Endpoints

CCI

CCI

The DAS28 (CRP) related Other Efficacy endpoints include:

- Change from baseline in DAS28 (CRP) by visit over time through Week 156.

- Proportion of participants who achieve a DAS28 (CRP) response by visit over time through Week 156.
- Proportion of participants who achieve a DAS28 (CRP) remission by visit over time through Week 156.

5.3.6.2.4. modified PsARC Related Endpoints

CCI

The modified PsARC related Other Efficacy endpoint is:

- Proportion of participants who achieve a response based on modified PsARC by visit over time through Week 156.

5.3.6.2.5. Enthesitis Related Endpoints

Enthesitis is an important feature of psoriatic arthritis and other spondyloarthropathies. In this study, enthesitis will be assessed by an independent joint assessor using the Leeds Enthesitis Index (LEI) (Healy 2008). CCI

- 
- 
- 

CCI

The enthesitis (LEI) related Other Efficacy endpoints include:

- Change from baseline in enthesitis score (LEI) by visit over time through Week 156 among the participants with enthesitis at baseline.
- Proportion of participants with resolution of enthesitis (LEI) by visit over time through Week 156 among the participants with enthesitis at baseline.

5.3.6.2.6. Dactylitis Related Endpoints

CCI

The dactylitis related Other Efficacy endpoints include:

- Change from baseline in dactylitis score by visit over time through Week 156 among the participants with dactylitis at baseline.
- Proportion of participants with resolution of dactylitis by visit over time through Week 156 among the participants with dactylitis at baseline.

5.3.6.2.7. mCPDAI Related Endpoints

CCI

CCI

Change from baseline in mCPDAI score measures the change in disease activity, where a negative change indicates an improvement and a positive change indicates a worsening.

Participants with low disease activity based on the mCPDAI score are those participants who have a mCPDAI score less than or equal to 3.2.

The mCPDAI related Other Efficacy endpoints include:

- Change from baseline in mCPDAI score by visit over time through Week 156.
- Proportion of participants with low disease activity based on mCPDAI by visit over time through Week 156

5.3.6.2.8. DAPSA Related Endpoints

[figure not shown]
CCI

CCI

The DAPSA related Other Efficacy endpoints include:

- Change from baseline in Disease Activity Index for Psoriatic Arthritis (DAPSA) score by visit over time through Week 156.
- Proportion of participants who achieve DAPSA low disease activity by visit over time through Week 156.
- Proportion of participants who achieve DAPSA remission by visit over time through Week 156.

5.3.6.2.9. MDA and VLDA

CCI

The MDA and VLDA related Other Efficacy endpoints include:

- Proportion of participants who achieve minimal disease activity (MDA) by visit over time through Week 156.
- Proportion of participants who achieve very low disease activity (VLDA) by visit over time through Week 156.

5.3.6.2.10. Method of Analysis

In general, descriptive statistics, such as mean, standard deviation (SD), median, inter quartile (IQ) range, minimum, and maximum for continuous variables, and counts and percentages for discrete variables will be used to summarize most data.

The **main analysis** for Other Efficacy endpoints related to reduction of signs and symptoms and physical function will be conducted using the Adjusted Composite Estimand. The ICE Strategy handling rules for the estimand will be applied first, after which the data handling rules for missing data will be applied. Specifically:

ICE Strategies for Adjusted Composite Estimand

For the Adjusted Composite Estimand, ICE categories 1, 2, 3, and 6 are incorporated as part of the endpoint using the composite strategy. This estimand acknowledges that a participant increasing their background PsA medications, electing to discontinue study intervention for reasons other than Natural Disaster or Major Disruption, or not entering the LTE due to lack of efficacy or worsening of PsA is an unfavorable outcome where participants who meet them prior to the visit will be considered as treatment failures at that visit and subsequently through the final efficacy visit. Participants meeting TF are considered non-responders for binary response endpoints, and to have no improvement (change from baseline = 0) for continuous endpoints, regardless of observed data.

This estimand also employs the hypothetical strategy. Primarily, regarding significant unplanned changes to study conduct as a result of Natural Disaster or Major Disruption. This estimand seeks to estimate the treatment effect of study intervention as if Natural Disaster or Major Disruption, as well as ICEs directly resulting from them, did not occur. Thus, for ICE category 4 all observed data after meeting the ICE through end of study will not be used and will be assumed to be MAR. For ICE category 5, observed data at the visit immediately subsequent to meeting the ICE will not be used and will be assumed to be MAR.

For participants experiencing multiple ICEs, an ICE in categories 1, 2, 3, and 6 (ie, using the composite strategy) will supersede an ICE in categories 4 or 5 (ie, using the hypothetical strategy).

These ICE strategies are also summarized in tabular form in Section [6.14](#).

Handling Rules for Missing Continuous Data for Adjusted Composite Estimand

1. **Missing data for any reason** will be assumed to be MAR. The data is not explicitly imputed, but is accounted for in the analysis model.

Handling Rules for Missing Binary Data for Adjusted Composite Estimand

1. Missing data due to Natural Disaster (caused site closure, site access restrictions, or lockdowns) or Major Disruption will be assumed to be MAR. The data is not explicitly imputed, but is accounted for in the analysis model.
2. Missing data due to not entering LTE for reasons OTHER THAN lack of efficacy, worsening of PSA will be assumed to be MAR. The data is not explicitly imputed, but is accounted for in the analysis model.
3. Missing data for any other reason will be assumed to be MAR but conservatively imputed as NR

Analysis Testing for Adjusted Composite Estimand

Statistical comparison between a guselkumab group (100 mg q4w or 100 mg q8w) and the placebo group will be performed by visit through Week 24 using the Mixed-Effect Model Repeated Measures (MMRM) model for continuous endpoints and the Generalized Linear Mixed Model (GLMM) for binary response endpoints (see Section 6.13). No treatment comparison will be performed after Week 24. For continuous endpoints, only descriptive summaries and LSmeans by study intervention and visit will be presented after Week 24 through Week 156; for binary endpoints, only descriptive summaries and model based response rates by study intervention and visit will be presented after Week 24 through Week 156.

ICE Strategies for Treatment Policy Estimand

For the Treatment Policy Estimand, the occurrence of ICEs is considered irrelevant. This estimand looks at the effect of assignment to intervention group irrespective of changes to background PsA medications, study intervention adherence, or study retention.

Handling Rules for Missing Data for Treatment Policy Estimand

1. **Missing data for any reason** will not be imputed, assumed to be MCAR.

Analysis Testing for Treatment Policy Estimand

A corresponding supportive analysis will be conducted using the Treatment Policy Estimand. For these analyses, the mFAS-UKR analysis set or further subset (if specified) will be used. For visits through Week 24, an ANCOVA model will be used for continuous endpoints, and the CMH test for treatment difference and 95% CI calculated based on Wald statistics will be used for the binary response endpoints. No treatment comparison will be performed after Week 24. For continuous endpoints, only descriptive summaries and LSmeans by study intervention and visit will be presented after Week 24 through Week 156; for binary endpoints, only descriptive summaries of response rates by study intervention and visit will be presented after Week 24 through Week 156.

Table 10 summarizes the analyses for supportive efficacy endpoints related to reduction of signs and symptoms and physical function, the methods for analyses, and the data handling rules used.

Table 10: Summary of Estimands, Analysis Sets, Data Handling Rules, and Analysis Methods for Endpoints of Signs & Symptoms and Physical Function

	Endpoint	Analysis Set	Missing Data Rules	Analysis Methods
ENDPOINTS BY VISIT THROUGH WEEK 24 AT WEEK-24 DBL, ADJUSTED COMPOSITE ESTIMAND				
1	Proportions of participants with ACR 20, ACR 50, and ACR 70 response	mFAS	NRI for MAR not due to Natural Disaster or Major Disruption	
 • Summarized descriptively • Response rates, and treatment difference in response rates and 95% CI and pvalue, based on GLMM

Table 10: Summary of Estimands, Analysis Sets, Data Handling Rules, and Analysis Methods for Endpoints of Signs & Symptoms and Physical Function

	Endpoint	Analysis Set	Missing Data Rules	Analysis Methods
2	ACR components	mFAS	-	
 Summarized descriptively LS mean (95% CI) for each intervention group
3	Change from baseline in ACR components	mFAS	-	
 Summarized descriptively LS mean (95% CI) for each intervention group
4	Percent change from baseline in ACR components	mFAS	-	
 Summarized descriptively LS mean (95% CI) for each intervention group
5	Change from baseline in HAQ-DI score	mFAS	-	
 Summarized descriptively LS mean (95% CI) for each intervention group, LS mean difference (95% CI) and p-values for differences between groups based on MMRM
6	Proportion of participants with HAQ-DI response	mFAS whose baseline HAQ-DI score ≥ 0.35	NRI for MAR not due to Natural Disaster or Major Disruption	
 Summarized descriptively Response rates, and treatment difference in response rates and 95% CI and pvalue, based on GLMM
7	Change from baseline in DAS28 (CRP)	mFAS	-	
 Summarized descriptively LS mean (95% CI) for each intervention group, LS mean difference (95% CI) and p-values for differences between groups based on MMRM
8	Proportion of participants with DAS28 (CRP) response	mFAS	NRI for MAR not due to Natural Disaster or Major Disruption	
 Summarized descriptively Response rates, and treatment difference in response rates and 95% CI and pvalue, based on GLMM
9	Proportion of participants with DAS28 remission	mFAS	NRI for MAR not due to Natural Disaster or Major Disruption	
 Summarized descriptively Response rates, and treatment difference in response rates and 95% CI and pvalue, based on GLMM
10	Proportion of participants with modified PsARC response	mFAS	NRI for MAR not due to Natural Disaster or Major Disruption	
 Summarized descriptively Response rates, and treatment difference in response rates and 95% CI and pvalue, based on GLMM

Table 10: Summary of Estimands, Analysis Sets, Data Handling Rules, and Analysis Methods for Endpoints of Signs & Symptoms and Physical Function

	Endpoint	Analysis Set	Missing Data Rules	Analysis Methods
11	Change from baseline in enthesitis score	mFAS with enthesitis at baseline	-	
 Summarized descriptively LS mean (95% CI) for each intervention group, LS mean difference (95% CI) and p-values for differences between groups based on MMRM
12	Proportion of participants with resolution of enthesitis	mFAS with enthesitis at baseline	NRI for MAR not due to Natural Disaster or Major Disruption	
 Summarized descriptively Response rates, and treatment difference in response rates and 95% CI and pvalue, based on GLMM
13	Change from baseline in dactylitis score	mFAS with dactylitis at baseline	-	
 Summarized descriptively LS mean (95% CI) for each intervention group, LS mean difference (95% CI) and p-values for differences between groups based on MMRM
14	Proportion of participants with resolution of dactylitis	mFAS with dactylitis at baseline	NRI for MAR not due to Natural Disaster or Major Disruption	
 Summarized descriptively Response rates, and treatment difference in response rates and 95% CI and pvalue, based on GLMM
15	Change from baseline in mCPDAI	mFAS	-	
 Summarized descriptively LS mean (95% CI) for each intervention group, LS mean difference (95% CI) and p-values for differences between groups based on MMRM
16	Proportion of participants with mCPDAI low disease activity	mFAS	NRI for MAR not due to Natural Disaster or Major Disruption	
 Summarized descriptively Response rates, and treatment difference in response rates and 95% CI and pvalue, based on GLMM
17	Change from baseline in DAPSA score	mFAS	-	
 Summarized descriptively LS mean (95% CI) for each intervention group, LS mean difference (95% CI) and p-values for differences between groups based on MMRM

Table 10: Summary of Estimands, Analysis Sets, Data Handling Rules, and Analysis Methods for Endpoints of Signs & Symptoms and Physical Function

	Endpoint	Analysis Set	Missing Data Rules	Analysis Methods
18	Proportion of participants with low disease activity or remission based on DAPSA	mFAS	NRI for MAR not due to Natural Disaster or Major Disruption	
 • Summarized descriptively • Response rates, and treatment difference in response rates and 95% CI and pvalue, based on GLMM
19	Proportion of participants with MDA	mFAS	NRI for MAR not due to Natural Disaster or Major Disruption	
 • Summarized descriptively • Response rates, and treatment difference in response rates and 95% CI and pvalue, based on GLMM
20	Proportion of participants with VLDA	mFAS	NRI for MAR not due to Natural Disaster or Major Disruption	
 • Summarized descriptively • Response rates, and treatment difference in response rates and 95% CI and pvalue, based on GLMM

‘-’ indicates no missing data rules to be applied

ENDPOINTS BY VISIT AFTER WEEK 24 THROUGH WEEK 48 AT WEEK-48 DBL, ADJUSTED COMPOSITE ESTIMAND

1, 2, 3 4, 6, 8, 9, 10, 12, 14, 16, 18, 19, 20	Same as through Week 24	Same as through Week 24	Same as through Week 24	
 • Summarized descriptively • Response rates by intervention group based on GLMM
5, 7 11, 13 15, 17	Same as through Week 24	Same as through Week 24	Same as through Week 24	
 • Summarized descriptively • LSMeans and 95% CI by intervention group based on MMRM model
21	Proportion of participants who maintained an ACR 20 response at Week 48	mFAS who achieved an ACR 20 response at Week 24	NRI for MAR not due to Natural Disaster or Major Disruption	
 • Summarized descriptively • Response rates by intervention group based on GLMM
22	Proportion of participants who maintained an ACR 50 response at Week 48	mFAS who achieved an ACR 50 response at Week 24	NRI for MAR not due to Natural Disaster or Major Disruption	
 • Summarized descriptively • Response rates by intervention group based on GLMM

Table 10: Summary of Estimands, Analysis Sets, Data Handling Rules, and Analysis Methods for Endpoints of Signs & Symptoms and Physical Function

	Endpoint	Analysis Set	Missing Data Rules	Analysis Methods
23	Proportion of participants who maintained an ACR 70 response at Week 48	mFAS who achieved an ACR 70 response at Week 24	NRI for MAR not due to Natural Disaster or Major Disruption	
 • Summarized descriptively • Response rates by intervention group based on GLMM
24	Proportion of participants who maintained HAQ-DI response at Week 48	mFAS who achieved HAQ-DI response at Week 24	NRI for MAR not due to Natural Disaster or Major Disruption	
 • Summarized descriptively • Response rates by intervention group based on GLMM

ENDPOINTS BY VISIT AFTER WEEK 48 THROUGH WEEK 96 AT WEEK-96 DBL, ADJUSTED COMPOSITE ESTIMAND

1, 2, 3 4, 6, 8, 9, 10, 12, 14, 16, 18, 19, 20	Same as through Week 24	Same as through Week 24	NRI for MAR not either: due to Natural Disaster or Major Disruption, OR not enter LTE due reason other than Lack of Efficacy/Worsening PsA	
 • Summarized descriptively • Response rates by intervention group based on GLMM
5, 7 11, 13 15, 17	Same as through Week 24	Same as through Week 24	Same as through Week 24	
 • Summarized descriptively • LSMeans and 95% CI by intervention group based on MMRM model
21	Proportion of participants who maintained an ACR 20 response at Week 96	mFAS who achieved an ACR 20 response at Week 24	NRI for MAR not either: due to Natural Disaster or Major Disruption, OR not enter LTE due reason other than Lack of Efficacy/Worsening PsA	
 • Summarized descriptively • Response rates by intervention group based on GLMM
22	Proportion of participants who maintained an ACR 50 response at Week 96	mFAS who achieved an ACR 50 response at Week 24	NRI for MAR not either: due to Natural Disaster or Major Disruption, OR not enter LTE due reason other than Lack of Efficacy/Worsening PsA	
 • Summarized descriptively • Response rates by intervention group based on GLMM

Table 10: Summary of Estimands, Analysis Sets, Data Handling Rules, and Analysis Methods for Endpoints of Signs & Symptoms and Physical Function

	Endpoint	Analysis Set	Missing Data Rules	Analysis Methods
23	Proportion of participants who maintained an ACR 70 response at Week 96	mFAS who achieved an ACR 70 response at Week 24	NRI for MAR not either: due to Natural Disaster or Major Disruption, OR not enter LTE due reason other than Lack of Efficacy/Worsening PsA	
 Summarized descriptively Response rates by intervention group based on GLMM
24	Proportion of participants who maintained HAQ-DI response at Week 96	mFAS who achieved HAQ-DI response at Week 24	NRI for MAR not either: due to Natural Disaster or Major Disruption, OR not enter LTE due reason other than Lack of Efficacy/Worsening PsA	
 Summarized descriptively Response rates by intervention group based on GLMM

ENDPOINTS BY VISIT AFTER WEEK 96 THROUGH WEEK 156 AT FINAL DBL, ADJUSTED COMPOSITE ESTIMAND

1, 2, 3 4, 6, 8, 9, 10, 12, 14, 16, 18, 19, 20	Same as through Week 24	Same as through Week 24	NRI for MAR not either: due to Natural Disaster or Major Disruption, OR not enter LTE due reason other than Lack of Efficacy/Worsening PsA	
 Summarized descriptively Response rates by intervention group based on GLMM
5, 7 11, 13 15, 17	Same as through Week 24	Same as through Week 24	Same as through Week 24	
 Summarized descriptively LSMeans and 95% CI by intervention group based on MMRM model
21	Proportion of participants who maintained an ACR 20 response at Week 156	mFAS who achieved an ACR 20 response at Week 24	NRI for MAR not either: due to Natural Disaster or Major Disruption, OR not enter LTE due reason other than Lack of Efficacy/Worsening PsA	
 Summarized descriptively Response rates by intervention group based on GLMM
22	Proportion of participants who maintained an ACR 50 response at Week 156	mFAS who achieved an ACR 50 response	NRI for MAR not either: due to Natural Disaster or Major Disruption, OR not enter LTE due reason other than Lack of	
 Summarized descriptively Response rates by intervention group based on GLMM

Table 10: Summary of Estimands, Analysis Sets, Data Handling Rules, and Analysis Methods for Endpoints of Signs & Symptoms and Physical Function

	Endpoint	Analysis Set	Missing Data Rules	Analysis Methods
		at Week 24	Efficacy/Worsening PsA	
23	Proportion of participants who maintained an ACR 70 response at Week 156	mFAS who achieved an ACR 70 response at Week 24	NRI for MAR not either: due to Natural Disaster or Major Disruption, OR not enter LTE due reason other than Lack of Efficacy/Worsening PsA	
 Summarized descriptively Response rates by intervention group based on GLMM
24	Proportion of participants who maintained HAQ-DI response at Week 156	mFAS who achieved HAQ-DI response at Week 24	NRI for MAR not either: due to Natural Disaster or Major Disruption, OR not enter LTE due reason other than Lack of Efficacy/Worsening PsA	
 Summarized descriptively Response rates by intervention group based on GLMM

**ENDPOINTS BY VISIT THROUGH WEEK 24 AT WEEK-24 DBL,
AFTER WEEK 24 THROUGH WEEK 48 AT WEEK-48 DBL,
AFTER WEEK 48 THROUGH WEEK 96 AT WEEK-96 DBL, AND
AFTER WEEK 96 THROUGH WEEK 156 AT FINAL DBL, USING TREATMENT POLICY
ESTIMAND AND THE mFAS-UKR ANALYSIS SET INSTEAD OF mFAS**

- The endpoints analyzed using the Adjusted Composite Estimand for corresponding visits/DBL are repeated here, except:
 - No imputation will be applied and all analyses will be based on observed data
 - Continuous endpoints will use ANCOVA instead of MMRM; binary response endpoints will use CMH test with CI based on Wald statistics instead of GLMM for visits up to and including Week 24

[figure not shown]
[figure not shown]

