5.3.2. General Data Handling Rules

Missing data will be handled depending on the assumed mechanism behind the missingness, whether the endpoint is a key endpoint, and the estimand being used. Handling rules are summarized in Table 6 below:

Table 6: Data Handling Rules for Missing Data

Estimand	Assumption	Continuous endpoints	Binary response endpoints
Adjusted Composite	MAR due to Natural Disaster or Major Disruption	Clinical Other Efficacy endpoints: not imputed but accounted for in MMRM model	Primary endpoint: imputed using Full Conditional Specifications (FCS) MI on continuous component scale then dichotomized Clinical Other Efficacy endpoints: not imputed but accounted for in GLMM
	MAR due to not entering LTE for reasons OTHER than Lack of Efficacy or Worsening of PsA	Clinical Other Efficacy endpoints: not imputed but accounted for in MMRM model	Clinical Other Efficacy endpoints: not imputed but accounted for in GLMM
	MAR NOT due to above reasons	Clinical Other Efficacy endpoints: not imputed but accounted for in MMRM model	Primary endpoint: conservatively imputed as non-response for consistency with historical studies Clinical Other Efficacy endpoints: conservatively imputed as non-response for consistency with historical studies
	Missing Not at Random (MNAR)	N/A	For tipping point analyses specifically: Sensitivity analysis with exhaustive assessment of all possible combinations of response status for missing data; Sensitivity analysis systematically assessing scenarios which deviate from MAR or MCAR assumption
Adjusted Treatment Policy	MAR	Radiographic endpoints: imputed using FCS MI; Radiographic sensitivity analysis: 2-step MI	Radiographic endpoints: imputed using FCS MI on continuous component scale then dichotomized
	MNAR	For tipping point analyses specifically: Sensitivity analysis systematically assessing scenarios which deviate from MAR or MCAR assumption	N/A
	MCAR	Radiographic endpoints: not imputed	Radiographic endpoints: not imputed
	MAR	Radiographic supplementary analyses: imputed using FCS MI	Clinical supplementary analyses: imputed using FCS MI on

Table 6: Data Handling Rules for Missing Data

Estimand	Assumption	Continuous endpoints	Binary response endpoints
Treatment Policy			continuous component scale then dichotomized

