5.3.6.1. Estimands

The estimand is composed of 5 components: Population, treatment, variable, intercurrent events, and population level summary. Of these, population, variable, and population level summary vary across the different endpoints, while treatment and intercurrent events are constant. For all endpoints, the treatments are placebo and the 2 guselkumab dose groups. Additionally, the definition of intercurrent events are defined below.

Adjusted Composite Estimand (for non-radiographic endpoints)

This estimand was previously defined for the primary analysis of ACR 20 response at Week 24 in Section 5.3.4.2. The ICEs are generalized across endpoints and for all efficacy visits below:

- **Intercurrent Events:**

1. Discontinued study intervention injections due to any reason **except** due to Natural Disaster or Major Disruption.
2. Initiated or increased the dose of non-biologic DMARDs (MTX, SSZ, HCQ, LEF) or oral corticosteroids over baseline for PsA.
3. Initiated protocol prohibited medications/therapies for PsA.
4. Discontinued study intervention injections due to Natural Disaster or Major Disruption.
5. Severe treatment non-compliance due to Natural Disaster or Major Disruption. This is defined for a given visit, when the total number of doses of study intervention missed due to Natural Disaster or Major Disruption exceeds 30% of the total protocol defined doses from Week 0 up to and including that visit. For Week 20, this amounts to ≥ 2 dose missed:

6. Decided to NOT enter the LTE due to lack of efficacy OR adverse event of worsening of PsA (only relevant after Week 48).

*Note that in the context of ICEs and missing data, the following are defined:

1. **Natural Disaster:** site closure, site access restrictions, or lockdowns caused by COVID-19.
2. **Major Disruption:** the disruption involving Ukraine and neighboring countries/territories beginning February 24, 2022

Treatment Policy Estimand (for non-radiographic endpoints)

This estimand was previously defined for the primary endpoint of ACR 20 response at Week 24 in Section 5.3.4.2 and for the change from baseline in modified vdH-S score at Week 24 in Section 5.3.5.1.2. The ICEs and their handling are generalized across endpoints and for all efficacy visits below:

- **Intercurrent Events:** the definition of the 6 categories of ICE are the same as the generalized Adjusted Composite Estimand in this Section.

Adjusted Treatment Policy Estimand (for radiographic endpoints only)

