6.14. Appendix 14: Summary of ICEs and ICE Strategy by Estimand

	ICE Category	ICE Strategy by Estimand		
		Adjusted Composite	Adjusted Treatment Policy	Treatment Policy
1	Discontinued study intervention injections due to any reason except Natural Disaster or Major Disruption.	
 Composite strategy Consider all subsequent data TF Priority = high 	
 Treatment Policy strategy No action taken, use all observed data Priority = low 	
 Treatment Policy strategy No action taken, use all observed data
2	Initiated or increased the dose of non-biologic DMARDs (MTX, SSZ, HCQ, LEF) or oral corticosteroids over baseline for PsA.	
 Composite strategy Consider all subsequent data TF Priority = high 	
 Treatment Policy strategy No action taken, use all observed data Priority = low 	
3	Initiated protocol prohibited medications/therapies for PsA.	
 Composite strategy Consider all subsequent data TF Priority = high 	
 Treatment Policy strategy No action taken, use all observed data Priority = low 	
4	Discontinued study intervention injections due to Natural Disaster or Major Disruption.	
 Hypothetical strategy Do not use all subsequent data (assuming MAR) Priority = low 	
 Hypothetical strategy Do not use all subsequent data (assuming MAR) Priority = high 	
5	Severe treatment non-compliance due to Natural Disaster or Major Disruption. Defined as: for a given visit, when the total number of doses of study intervention missed due to Natural Disaster or Major Disruption exceeds 30% of the total protocol defined doses from Week 0 up to and including that visit. For Weeks 20, this amounts to ≥ 2 dose missed	
 Hypothetical strategy Do not use data at subsequent visit (assuming MAR) Priority = low 	
 Hypothetical strategy Do not use data at subsequent visit (assuming MAR) Priority = high 	

	ICE Category	Adjusted Composite	ICE Strategy by Estimand	Treatment Policy

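### After Week 48, an adverse event other than worsening PsA is a treatment failure if it leads to discontinuation, but is assumed missing at random if it leads an eligible participant not to enter the extension

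*SAP*

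**What the plan says.** SAP 5.3.6.1 lists six intercurrent events (ICEs) for the clinical Other Efficacy endpoints. Two concern stopping study drug outside a disaster or disruption.

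- **ICE 1** is worded in Appendix 14 (6.14) as "Discontinued study intervention injections due to any reason except Natural Disaster or Major Disruption".
- **ICE 6** is "Decided to NOT enter the LTE due to lack of efficacy OR adverse event of worsening of PsA", and applies only after Week 48.

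SAP 5.3.6.2.10 handles both by the composite strategy. Participants who meet them "will be considered as treatment failures at that visit and subsequently through the final efficacy visit": non-responder for binary endpoints, change = 0 for continuous ones.

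The same section then gives three rules for missing binary data. Rule 1 makes disaster and disruption cases MAR. Rule 2 covers the remaining non-entrants: "Missing data due to not entering LTE for reasons OTHER THAN lack of efficacy, worsening of PSA will be assumed to be MAR"; the data are not imputed and are left to the GLMM. Rule 3 covers everything else: "Missing data for any other reason will be assumed to be MAR but conservatively imputed as NR". Table 6 (5.3.2) repeats rule 2 as "MAR due to not entering LTE for reasons OTHER than Lack of Efficacy or Worsening of PsA", for MMRM and GLMM alike. The post-Week-48 rows for binary endpoints in Tables 10 to 13 carry the same exception. On order, the SAP states: "The ICE Strategy handling rules for the estimand will be applied first, after which the data handling rules for missing data will be applied".

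**The concern.** Not entering the LTE is a way of stopping study drug. The Week 48 administration belongs to the LTE (protocol 1.3, Table 1, footnote y), so a non-entrant has no dose at or after Week 48. ICE 6 recognises this by making some non-entry a failure, but the only adverse event it names is worsening PsA. Non-entry because of any other adverse event falls to rule 2.

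A tolerability stop recorded as discontinuation thus counts as failure through Week 156, while a stop for the same event that takes the form of declining the LTE does not. Rule 3 sharpens the contrast: a visit missed for no known reason is non-response, while a known adverse-event stop at Week 48 is not.

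At stake is the reading of the long-term response rates, including maintenance of ACR and HAQ-DI response at Weeks 96 and 156. The protocol's dose justification (4.3) includes both regimens partly to allow a relative benefit-risk assessment of q4w, so a reader will compare these rates across arms even though no formal comparison is planned.

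**Working it through.** The documents give no figure on this point, so there is none to reproduce. The check traces the rules and then does the arithmetic.

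**Step 1. Tracing one adverse event, not worsening PsA**

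| How the stop occurs | Rule that applies | Value at later visits |
|---|---|---|
| Recorded as discontinuation of injections, before Week 48 or during the LTE | ICE 1, composite | Non-responder, or change = 0 |
| Eligible at Week 48, does not enter the LTE because of the event | Not ICE 6; missing-data rule 2 | MAR, left to GLMM or MMRM |
| As the row above, but the event is worsening PsA | ICE 6, composite | Non-responder, or change = 0 |

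**Step 2. Does ICE 1 already absorb the second row?** ICE rules come first, and ICE 1 read literally covers any stop. But if every non-entry were ICE 1, ICE 6 would be redundant and rule 2 would have nothing left to cover. The SAP therefore treats non-entry as a separate event. It does not say how adverse-event-driven non-entry should be classified.

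**Step 3. Does another analysis count these people as failures?** No.
- The Treatment Policy analysis of these endpoints uses observed data only, under MCAR (5.3.6.2.10).
- The tipping-point analyses cover only the primary and key secondary endpoints (5.3.2.1).
- The GLMM contains treatment, visit by treatment, and strata (6.13), with no adverse-event term.
- The disposition summaries (5.2) count LTE entry but do not list reasons for non-entry.

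**Step 4. Direction and size, binary endpoints.** Let:
- d = share of the arm (for maintenance endpoints, of its Week 24 responders) not entering because of an adverse event other than worsening PsA; assumed.
- p = response rate among everyone else; assumed.
- q = response probability the model implies for the non-entrants; assumed.

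Rate if they are failures: p(1 − d). Rate if they are MAR: p(1 − d) + qd. Difference: d × q, which is positive whenever q > 0.

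Example with p = q = 60% and d = 2%: failure rate 0.60 × 0.98 = 58.8%; MAR rate 58.8% + 0.02 × 60% = 60.0%; difference 1.2 points. The 60% is the planning rate for ACR 20 at Week 24 (SAP 3.1.1), borrowed for illustration and not a long-term rate.

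| d | q = 40% | q = 60% | q = 80% |
|---|---|---|---|
| 0.5% | 0.2 | 0.3 | 0.4 |
| 1% | 0.4 | 0.6 | 0.8 |
| 2% | 0.8 | 1.2 | 1.6 |
| 5% | 2.0 | 3.0 | 4.0 |

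Entries are percentage points. A GLMM works on the logit scale, so its fitted rate will follow this only approximately. Stricter endpoints such as ACR 70 or VLDA may have a lower q and so a smaller effect.

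**Step 5. Continuous endpoints.** The contrast is change = 0 against MAR in the MMRM. The documents allow no size to be put on it.

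**Step 6. What is untouched.** Radiographic endpoints use treatment policy for ICEs 1 and 6 (5.3.6.6.2), so this mismatch does not arise. The primary endpoint, the key secondary endpoint and every Week 24 comparison precede Week 48.

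**The case against.** The strongest reply is that most adverse-event stops are caught already. ICE 1 covers stopping for any non-disruption reason and is applied first. Protocol 7.1 requires discontinuation for several safety events, and the LTE is open only to people who have not discontinued. That stands for any stop recorded as a discontinuation at or before Week 48. A reader might infer that every adverse-event stop at Week 48 is treated as MAR; the documents do not support that. The gap concerns people still eligible at Week 48 who decline because of an adverse event other than worsening PsA.

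Second, the stated estimand includes ICE 6 as written, and the SAP applies it consistently. A reader might infer that the long-term rates are biased for their own estimand. They are not: they are raised only relative to a composite that treats adverse-event stops alike. Declining an optional extension also differs from abandoning treatment, since a non-entrant who completes Weeks 48 and 60 has completed the main study (protocol 4.4). That is a fair reason to leave personal-choice non-entry as MAR. It is weaker for an adverse event, because ICE 6 already makes one kind of adverse-event non-entry a failure.

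Third, aligning adverse events does not remove every difference from ICE 1: a personal-choice stop at Week 44 stays a failure and personal-choice non-entry stays MAR. That is true, and the proposal does not claim otherwise.

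Fourth, no non-entry rate is given. It would be tempting to call Week 48 the largest exit point, or to say the rates are materially overstated, but nothing in the documents supports either.

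**Conclusion.** The inconsistency is in the text and holds in a limited form. The rise of d × q in post-Week-48 binary rates is certain in direction, against a composite applied consistently to adverse-event stops. Its size is unknown: the 0.2 to 4.0 point range rests wholly on the assumed d and q, and the true value may lie at or below the low end because recorded discontinuations are already ICE 1. Whether it differs by arm cannot be told from the documents. The affected results are descriptive, with no treatment comparison after Week 24 and no multiplicity control, so no confirmatory conclusion depends on them. This is a minor point, worth correcting because it is cheap and because handling now turns on how a site records the stop.

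**What to change.** 1. In SAP 5.3.6.1, 5.3.6.2.10 and 6.14, extend ICE 6 to non-entry because of lack of efficacy or any adverse event. Alternatively, state that non-entry driven by an adverse event is ICE 1.
2. Narrow the MAR rule in 5.3.6.2.10, Table 6 and the post-Week-48 rows of Tables 10 to 13 to non-entry for reasons that are neither efficacy nor an adverse event.
3. Add reasons for non-entry, by arm, to the disposition summaries in 5.2, so that d can be read directly.

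The cost is SAP wording and one table. Rule 2 already requires non-entry to be classified by reason. The downside is slightly lower long-term response rates.
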